The ***secondary objectives*** are to determine the impact of HCR compared to PCI on health status and quality of life.

BACKGROUND AND SIGNIFICANCE

Importance of the Study

The increasing prevalence of coronary artery disease (CAD), advances in coronary artery bypass grafting (CABG), PCI, and concomitant medical therapy, and the costs of revascularization have resulted in rising interest regarding the appropriate indications and alternatives for coronary revascularization. The 2009 ACCF/SCAI/STS/AATS/ AHA/ASNC Appropriateness Criteria for Coronary Revascularization document that for patients with 3-vessel disease requiring revascularization, CABG is rated as appropriate while revascularization by PCI is rated as uncertain.¹ Moreover, the recent SYNTAX trial demonstrated that CABG was superior to PCI with first generation drug eluting stents (DES) for patients with 3- vessel disease and/or left main coronary artery (LM) disease.² However, the SYNTAX trial results were driven by the repeat revascularization component of the primary composite endpoint (lower for CABG), and divergence with the outcomes of the stroke component (higher for CABG) has led to differences in interpretation of the overall results.

These differences in interpretation, coupled with strong patient preferences for the lower level of invasiveness, a potentially lower stroke risk, and faster recovery have driven the widespread adoption of PCI. At the same time, CABG has been shown to provide improved long-term durability, superior long term symptom relief, fewer repeat interventions and higher rates of survival.²⁻⁴ Integrating the positive features of both PCI and CABG has been the fundamental rationale of “hybrid” coronary revascularization.

Hybrid coronary revascularization is the intended combination of CABG and PCI. The HCR strategy combines grafting of the left anterior descending artery (LAD) coronary artery using the left internal mammary artery (LIMA) and PCI of non-left anterior descending coronary artery (LAD) coronary stenoses. Essentially, stents are substituted for saphenous vein grafts (SVG) for non-LAD lesions, and the surgical LIMA to LAD bypass is performed, ideally through a limited access, minimally traumatic approach. The rationale for choosing HCR over PCI or CABG alone stems from a number of observations:

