The primary endpoint of this trial is MACCE over 5 years following randomization. For the purpose of this trial, the components of MACCE include (1) all-cause mortality, (2) myocardial infarction, (3) stroke, and (4) unplanned revascularization. The primary objective of this trial is to determine whether hybrid coronary revascularization is associated with a reduction in MACCE compared to PCI with metallic DES.

Secondary Endpoints

The secondary endpoints of the trial (measured at 30 days post procedure, 12, 24, 36, 48, and 60 months, unless otherwise specified) include:

Cardiovascular Events

- MACCE at 30 days post procedure, and 12, 24, 36, 48 months
- Individual components of MACCE: All-cause mortality, myocardial infarction, stroke, unplanned revascularization
- Ischemia-driven revascularization
- Cardiovascular and non-cardiovascular mortality

Hospitalizations

- Re-hospitalization (all-cause and cardiovascular)

Health Status

- Angina Score (Canadian Cardiovascular Society Classification [CCSC])
- Quality of Life (QoL) (Short Form 12 Health Survey [SF-12}, European Quality of Life Scale [EuroQoL])

Cost-effectiveness

- Costs
- Quality-adjusted life expectancy

STUDY POPULATION

The patient population for this trial consists of adult patients with multi-vessel coronary artery disease involving the Left Main (LM) and/or Left Anterior Descending (LAD) arteries, and a clinical indication for revascularization, who are candidates for both HCR and PCI with metallic DES.

Eligibility Criteria

All patients who meet all inclusion criteria and no exclusion criteria will be eligible for the trial

Inclusion Criteria

1. Signed informed consent, inclusive of release of medical information, and Health Insurance Portability and Accountability Act (HIPAA) documentation (US sites)
2. Age \geq 18 years
3. Clinical indication for coronary revascularization
4. Coronary anatomy requiring revascularization as follows⁽²⁾
 - Multivessel CAD involving the LAD (proximal or mid) *and/or* LM (ostial, mid-shaft or distal) *with* at least 1 other epicardial coronary artery requiring treatment (LCX or RCA), OR
 - Single vessel disease involving the LAD and a major diagonal, with both requiring independent revascularization with at least one stent if randomized to HCR and stents for both the LAD and diagonal if randomized to multivessel PCI

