Symptomatic graft stenosis or occlusion requires angiographic confirmation of a DS $\geq 50\%$, and the presence of at least one of the following criteria: i) A positive functional study corresponding to the area served by the target lesion; or ii) Ischemic ECG changes at rest in a distribution consistent with the target vessel; or iii) Typical ischemic symptoms referable to the target lesion; or iv) IVUS of the target lesion with a minimal lumen area (MLA) of $\leq 4 \text{ mm}^2$; or v) FFR of the target lesion ≤ 0.80 or iFR of the target lesion ≤ 0.90 .
Intervention on the LIMA, LIMA-LAD distal anastomosis or LAD triggered by routine LIMA angiography prior to a staged PCI will also be considered to meet the criteria for symptomatic graft stenosis or occlusion.
The adjudicated rates of symptomatic graft stenosis or occlusion of the LIMA to the LAD in the HCR arm will be compared to the rate of angiographic definite stent thrombosis of LAD stents in the PCI arm.

Hospitalizations (non-adjudicated)

- Re-hospitalization will be assessed and classified as all-cause or cardiovascular (further subdivided as due to cardiac arrest, acute MI, heart failure or cardiogenic shock, other cardiovascular causes, or bleeding).

Bleeding (non-adjudicated)

- Site assessed bleeding complications will be reported using the Bleeding Academic Research Consortium (BARC) Scale²⁶:
 - **Type 0:** no bleeding
 - **Type 1:** bleeding that is not actionable and does not cause the patient to seek unscheduled performance of studies, hospitalization, or treatment by a healthcare professional; may include episodes leading to self-discontinuation of medical therapy by the patient without consulting a healthcare professional
 - **Type 2:** any overt, actionable sign of hemorrhage (eg, more bleeding than would be expected for a clinical circumstance, including bleeding found by imaging alone) that does not fit the criteria for type 3, 4, or 5 but does meet at least one of the following criteria: (1) requiring nonsurgical, medical intervention by a healthcare professional, (2) leading to hospitalization or increased level of care, or (3) prompting evaluation (this does not apply to routine evaluation of chest tube drainage).
 - **Type 3**
 - **Type 3a**
 - Overt bleeding plus hemoglobin drop of 3 to 5 g/dL (corrected for transfusion: 1 U packed red blood cells or 1 U whole blood = 1 g/dL hemoglobin or 3% hct), OR
 - Any transfusion with overt bleeding
 - **Type 3b**

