The following will be collected for all hospitalizations required to complete the original planned revascularization strategy, if staged.

Medications

Data regarding medication use within 24 hours prior to, during the revascularization procedure or within 24 hours after the procedure, including antiplatelet and antithrombin agents, beta blocker, and ACE inhibitors, ARBs, aldosterone antagonists, and statins, will be collected at the sites. This data will be collected whenever possible for all subsequent revascularization procedures.

Laboratory Assessment

Data partially extracted from the STS Registry database

Data regarding the following laboratory values after the index coronary revascularization will be extracted from the clinical registry databases:

- CK MB and/or Troponin I or T (ng/mL)

PCI Procedure

Data regarding the index PCI procedure(s) will be provided by the site coordinators. Information to be collected includes, but is not limited to, the status of the procedure (e.g., elective, urgent, emergency, salvage), indications for the procedure, the percutaneous intervention(s) performed, and intra and post-procedural events.

Index Surgical Procedure

Data partially extracted from the STS registry database; HCR Group ONLY. Additional data to be supplied by cardiac surgical investigator

Data regarding the surgical intervention for the HCR procedure will be extracted from the STS dataset, including but not limited to the status of the procedure (e.g., elective, urgent, emergent, and emergent salvage), details regarding the anesthesia and intra-operative interventions, bypass pump use, conduit and harvest technique, anastomoses, concomitant procedures, and intra-operative blood use and complications if applicable. Modest additional

Hospitalization & MACCE Events

Limited information about the index revascularization procedure(s) and hospitalization will be extracted from the STS registry dataset including length of stay, transfusion requirements, repeat procedures, and discharge disposition when possible. Information regarding MACCE events that occur during study-procedure related hospitalizations will also be extracted from the STS registry when possible. Limited source documentation pertaining to the MACCE event will be collected and uploaded into the EDC as detailed in the trial Manual of Procedures (MOP).

Index Hospital Costs

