Cardiovascular Events

Secondary cardiovascular events include MACCE at each data collection time point; individual components of MACCE (all-cause mortality, stroke, myocardial infarction, unplanned revascularization,); cardiovascular and non-cardiovascular mortality, ischemia-driven revascularization, and other cardiovascular events.

MACCE at each time point, individual components of MACCE, cardiovascular and non-cardiovascular mortality, , ischemia-driven revascularization other cardiovascular endpoints such as stent thrombosis and symptomatic graft stenosis or occlusion, and bleeding events will be analyzed using the stratified log-rank statistic in the manner of the primary outcome. Unplanned revascularization, stroke, MI, and cardiovascular mortality may not occur because death from any cause precedes the event, thus it is possible that censoring patients from all-cause mortality may lead to biased estimates when analyzing time to first event of these outcomes. As a sensitivity analysis, competing risks analysis using the methods of Gray²⁹ and Fine and Gray³⁰ will be used to calculate cause-specific cumulative incidence. Gray and Fine's test will be compared with the log-rank test for the treatment group effect, and the cumulative incidence curve will be compared to the Kaplan-Meier curve.

For unplanned and ischemia-driven revascularizations, a Poisson regression model will be used to assess differences in the rate of revascularization between groups. Time to death will be described by Kaplan-Meier curves and differences between randomization groups assessed via the stratified log-rank test. Mortality analyses will be conducted for both cardiovascular and non-cardiovascular mortality.

Hospitalizations

All cause and cardiovascular re-admissions will be recorded. A Poisson regression model will be used to compare the rate of readmission between groups for any cause, and specifically for cardiovascular hospitalizations.

Health Status

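### Readmission rates are tested only by Poisson regression, with no stated allowance for extra-Poisson variation between patients

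*Combined protocol and SAP*

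**What the plan says.** The Hospitalizations paragraph under Analysis of Secondary End-points states: "A Poisson regression model will be used to compare the rate of readmission between groups for any cause, and specifically for cardiovascular hospitalizations". This is the only test planned for readmission.

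The Cardiovascular Events paragraph just above uses the same model for repeat procedures: "For unplanned and ischemia-driven revascularizations, a Poisson regression model will be used to assess differences in the rate of revascularization between groups". Revascularization also belongs to a list of endpoints that "will be analyzed using the stratified log-rank statistic in the manner of the primary outcome", and unplanned revascularization has a further check: "As a sensitivity analysis, competing risks analysis using the methods of" Gray and of Fine and Gray. Re-hospitalization is in neither group.

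The endpoint appears under Secondary Endpoints as "Re-hospitalization (all-cause and cardiovascular"). The definitions section marks it as non-adjudicated: "Re-hospitalization will be assessed and classified as all-cause or cardiovascular". The Objectives section does not mention it; the secondary objectives "are to determine the impact of HCR compared to PCI on health status and quality of life".

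The Analysis Plan sets two-sided tests at 0.05 for all hypothesis testing.

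**The concern.** A Poisson model assumes that the variance of the counts equals their mean. Readmissions are repeatable, and the plan records them without limiting them to the first. When some patients are readmitted more readily than others, the variance exceeds the mean. The rate ratio is still estimated correctly, but its model-based standard error is too small.

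The plan itself gives reason to expect such differences. Eligibility spans stable disease and biomarker-positive acute coronary syndrome. The anatomical strata run from LAD and diagonal only to LAD or left main plus both other vessels. The cost-effectiveness section individualizes event rates and bootstraps its model to reflect differences between patients. The readmission test makes no comparable allowance.

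At stake is a spurious difference in readmission between the arms, with no second planned test of that endpoint to set against it.

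**Working it through.** **Search for a provision elsewhere.** Mixed-effects models are tied to quality of life and to a general statement under Missing Data. The bootstrap belongs to the cost-effectiveness model. Exact Poisson intervals, under Safety Analysis, are for MACCE components. None covers the variance of readmission counts.

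**Inputs from the documents.** 2354 patients, 1:1, so 1,177 per arm; 5 years of follow-up; 15% lost by the end of the study; two-sided alpha 0.05.

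**Assumed inputs.** The readmission rate r per patient-year; the variance k of a gamma frailty with mean 1; losses spread uniformly over 5 years.

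**Formula.** The variance-to-mean ratio is φ = 1 + k × r × E[t²]/E[t]. The true type I error of the model-based Wald test is 2 × (1 − Φ(1.96/√φ)).

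- The plan's figure first: k = 0 gives φ = 1 and a type I error of 0.050, the stated alpha.
- E[t] = 0.85 × 5 + 0.15 × 2.5 = 4.625 years.
- E[t²] = 0.85 × 25 + 0.15 × 25/3 = 22.5.
- E[t²]/E[t] = 22.5/4.625 = 4.865.

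**Results at 60 months**, with a simulation of 8,000 runs per setting (Monte Carlo standard error about 0.24 percentage points at 5%):

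| r | k | φ | Type I, formula | Type I, simulated | Type I, robust errors | Coverage of model-based 95% interval | Robust/model SE |
|---|---|---|---|---|---|---|---|
| 0.2 | 0 | 1.00 | 5.0% | 5.0% | 5.1% | 95.1% | 0.999 |
| 0.05 | 0.5 | 1.12 | 6.4% | 6.5% | 5.1% | 93.5% | 1.058 |
| 0.2 | 0.5 | 1.49 | 10.8% | 10.3% | 4.8% | 89.7% | 1.218 |
| 0.3 | 1 | 2.46 | 21.1% | 21.0% | 4.6% | 79.0% | 1.566 |

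Four further settings gave 8.4% (r = 0.1, k = 0.5), 10.4% (0.1, 1), 16.3% (0.2, 1) and 13.1% (0.3, 0.5). Robust errors stayed at 4.6-5.3% in all eight. A separate simulation with exponential losses and 4,000 runs agreed: 11.4% at r = 0.2, k = 0.5 and 21.0% at r = 0.3, k = 1.

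**Shorter horizons.** Secondary endpoints are also listed at 30 days and at yearly visits. With complete follow-up to time T, E[t²]/E[t] = T.

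- 12 months: r = 0.2, k = 0.5 gives φ = 1.10 and 6.2%; r = 0.3, k = 1 gives φ = 1.30 and 8.6%.
- 30 days (T = 30/365 = 0.082): φ = 1.008 and 1.025, so 5.1% and 5.3%.

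**Revascularization.** With an assumed mean of 0.10 to 0.20 procedures per patient and k of 0.5 to 1, the share with at least one is 1 − (1 + k × mean)^(−1/k), or 9% to 17%. That fits inside the 25% composite rate planned for the PCI group. Simulated type I error is 5.6% to 7.5%.

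**The case against.** The strongest reply is that this is an omission and not an error. Naming Poisson regression does not rule out robust standard errors, and with no heterogeneity the test is right as written. Harm needs two conditions: patients who differ in rate, and an analyst who takes the model's default errors. The documents prove neither. This stands as a limit on the claim. It does not remove the claim, because default errors are the ordinary reading of the sentence, and leaving the variance open allows the choice to be made after the data are seen in an unmasked trial.

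A reader might infer that this trial's readmission test will reject falsely 10% or 20% of the time. The documents do not support that. They supply no rate and no dispersion, and the Hospitalizations paragraph does not say which horizon is tested. The larger figures belong to 60 months and to the higher assumed values. Cardiovascular readmissions are a subset of all readmissions, so at equal frailty variance their inflation is no larger. The simulations also ignore death, which shortens follow-up, and follow-up beyond 5 years, which lengthens it; these pull in opposite directions.

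The planned univariate description could make marked overdispersion visible if readmissions are tabulated as counts. That would reveal the problem without correcting the test.

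A log follow-up offset is arguably implied by comparing rates. Stating it costs nothing.

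**Conclusion.** The point holds as a gap that should be closed. Poisson regression is the only planned test of readmission, and nothing in the plan allows for extra-Poisson variation. If patients differ in rate and default errors are used, the nominal 5% level is exceeded. The excess at 60 months ranges from slight (about 6%) to large (21%) over the assumed values, is smaller at 12 months, and is close to nil at 30 days.

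For revascularization the same gap matters less: the assumed inflation is small and a stratified log-rank test is also planned.

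A reader might extend this to the trial's main conclusion. The documents do not support that: the primary MACCE comparison is a stratified log-rank test of time to first event, and neither it, the 530-event target nor the interim safety rule uses readmission counts.

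**What to change.** In the Hospitalizations paragraph, specify Poisson regression with patient-level robust (sandwich) standard errors and log follow-up time as offset, for all-cause and cardiovascular readmission. Negative binomial regression with the same offset is an acceptable alternative if it is named in advance. Apply the same variance method to the revascularization rates in the Cardiovascular Events paragraph.

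The cost is SAP wording; no new data are needed. Intervals widen only as far as heterogeneity exists: by a factor of 1.00 with none, and by 1.06, 1.22 and 1.57 in the other three tabulated cases. Without heterogeneity, power is practically unchanged between robust and model-based errors: 73.3% against 73.5% at 0.1 per year and rate ratio 0.85, and 66.8% for both at 0.2 per year and rate ratio 0.90.

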Randomization

Must be completed

- (a) within 90 days of the 3-vessel qualifying angiogram for patients identified in the setting of a diagnostic angiogram, or*
- (b) within 90 days following the qualifying 3-vessel angiogram for patients also undergoing a PCI of a non-LAD and non-LM vessel prior to randomization. (See table under Randomization Section)*

The first study intervention is recommended to be performed within 72 hours post randomization and must be performed within 14 days following randomization.

Randomization to the treatment assignment will be generated by the EDC system once the checklist of inclusion and exclusion criteria has been completed and verified and the planned revascularization strategy form has been completed. For the purpose of the primary analysis, patients are considered enrolled in the study once they are randomized and an identification code is generated.

Revascularization Plan

Prior to randomization

The surgical and percutaneous revascularization plan will be described for both HCR and PCI-only revascularization *prior to randomization*. This plan may be revised within 24 hours of the first procedure after randomization to reflect procedural complications, should they occur. Any revascularization procedures deviating from the final revascularization plan in place 24 hours after the first procedure will be considered unplanned revascularization procedures.

Note: Any revascularization procedure that is done during a planned revascularization procedure will NOT be considered an unplanned procedure. E.g.: planned minimally invasive LIMA-LAD procedure becomes complicated by inferior ischemia requiring conversion to an open procedure and RCA bypass; or planned PCI after minimally invasive

LIMA-LAD procedure demonstrated LIMA-LAD graft occlusion requiring PCI; or planned PCI of the LCX results in a LM dissection requiring a LM stent. However, CABG complications that result in separate **unplanned** PCI or CABG procedures, and PCI complications that result in separate **unplanned** PCI or CABG procedures, will be considered unplanned procedures and endpoint events.

Angina Class - Canadian Cardiovascular Society Classification (CCSC)

Following determination of eligibility and within 14 days prior to randomization

The presence of angina will be assessed, and when present, classified according to the CCSC scale and documented on this form. CCSC classification scheme is detailed in Appendix I.

NYHA Class

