At 6 (± 1), 12 (± 1), 18 (± 1), 24 (± 1), 30 (± 1), 36 (± 1), 42(± 1), 48 (± 1), 54 (± 1), and 60 (± 1) months post-randomization, via centralized DCC telephone follow-up (when allowed by local

The presence of angina will be assessed by the DCC research nurse, and when present, classified according to the CCSC scale and documented on this form. CCSC classification scheme is detailed in Appendix I.

Quality of Life

At 12 (±1), 24 (±1), 36(±1), 48 (±1), and 60 (±1) months post-randomization, via centralized DCC telephone follow- up (when allowed by local IRB/REBs)

The SF-12 and EuroQoL will be administered annually, either by phone from the DCC research nurse or site coordinator, or via electronic patient portals, including electronic QoL surveys that can be utilized for all patients with computer, tablet or smart phone capability. The electronic forms will also be accessible for patient reporting via a password protected portal on the HCR Trial website.

Costs

Collected at 12 (±1), 24 (±1), 36 (±1), 48 (±1), and 60 (±1) months post-randomization, via electronic transfer from UHC database and UB forms

Medical costs were defined as hospital costs, physician fees, outpatient procedure costs, the cost of prescription drugs, and the cost of rehabilitation incurred after the index hospitalization. Medical claims associated with any hospital stay and outpatient service in participating sites are collected annually. Cost data will be extracted from the UHC operational database system for member sites, and from UB medical claims forms for sites without UHC membership. UB medical claims will be converted to costs using the same methodology as used by UHC to estimate costs using center-specific ratios of cost to charges. These ratios will be based on the annual Medicare costs reports submitted by participating study sites to Medicare. Multivariable imputation algorithms will be used to impute costs for patient-reported out of network hospital stays. Physician fees will be based on collected MACCE and length of stay data and the Medicare fee schedule. Resource use associated with prescribed medication and the rehabilitation of myocardial infarction and stroke will be estimated based on patient-reported information and will be converted into dollars using reimbursements from Centers for Medicare and Medicaid Services costing reports

Event Driven Data Collection

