Health status will be measured by Angina Score (Canadian Cardiovascular Society Classification [CCSC]) and by QoL surveys (SF-12 and EuroQOL). The distribution of CCSC angina class will be presented for each randomization arm and compared using a chi-squared test at each time point. Quality of life will be measured using the SF-12 and EuroQol. Quality of life will be analyzed longitudinally using mixed effects models.^{31, 32, 33} Log-transformations will be used, if necessary to normalize the variables or stabilize the variance. These models will be used to predict outcome given treatment group and time. The interaction between treatment and time will be used to determine the difference between the two arms over time.

Cost-effectiveness

A cost-effectiveness analysis will be performed from an overall healthcare system perspective. Costs associated with hospitalizations and outpatient services will be estimated from collected medical claim data using center-specific ratios of cost to charges. Multivariable imputation algorithms will be used to impute costs for patient-reported out of network MACCE related hospitalizations. Community-based health state preferences will be estimated from the trial's EuroQOL data using an algorithm developed for the U.S. general population.³⁴

We will subsequently develop an individual-level decision model, which will predict and extrapolate the overall survival, quality of life, and costs per trial participant as a function of randomization and MACCE. With the decision model we will compare the two scenarios: HCR vs. PCI by rerunning the randomized trial "in silico". In this re-simulated trial, each of the 2354 patients will be virtually exposed to both scenarios. Subsequently, each patient's life course according to an intention-to-treat principle is modeled by microsimulation while individualizing event rates, quality of life and costs.

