APPENDIX I: Canadian Cardiovascular Society Classification

Overview:

The Canadian Cardiovascular Society Classification of angina pectoris separates patients with anginal symptoms into groups based on the severity of their symptoms. The classification uses the extent of limitation on daily activities and the kind of physical activity which precipitates the anginal episode.

| Clinical Findings | Features | Grade |
|---|---|-------|
| No limitation of ordinary activity | Ordinary physical activity (such as walking or climbing stairs) does not cause angina. Angina may occur with strenuous rapid or prolonged exertion at work or recreation. | I |
| Slight limitation of ordinary activity | 
Angina may occur with
 
 • Walking or climbing stairs rapidly; • Walking uphill; • Walking or stair climbing after meals or in the cold in the wind or under emotional stress, or only during the few hours after awakening. • Walking more than 2 blocks on the level at a normal pace and in normal conditions • Climbing more than 1 flight of ordinary stairs at a normal pace and in normal conditions | II |
| Marked limitation of ordinary physical activity | 
Angina may occur after
 
 • Walking 1-2 blocks on the level or • Climbing 1 flight of stairs in normal conditions at a normal pace | III |
| Unable to carry on any physical activity without discomfort | Angina may be present at rest. | IV |

Campeau L. Grading of angina pectoris (Letter to the Editor). *Circulation*. 1976; 54: 522-523.

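### The ordered CCSC angina class is compared by a chi-squared test that takes no account of order, gives no effect estimate and does not use the baseline class

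*Combined protocol and SAP*

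**What the plan says.** Health status is a secondary objective: the secondary objectives "are to determine the impact of HCR compared to PCI on health status and quality of life" (Objectives). CCSC angina score is one of the two health-status endpoints, "measured at 30 days post procedure, 12, 24, 36, 48, and 60 months, unless otherwise specified" (Endpoints, Secondary Endpoints). The Data Collection Schedule has CCSC at 30 days and then every six months to month 60, which is 11 post-baseline visits.

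The analysis is one sentence in the Analytical Plan, Health Status: the class distribution is shown by arm and "compared using a chi-squared test at each time point". It names no trend score, covariate, effect estimate or degrees of freedom. The same paragraph gives SF-12 and EuroQol a longitudinal mixed-effects model.

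Appendix I states that the scale "separates patients with anginal symptoms into groups based on the severity of their symptoms", in grades I to IV. The baseline form, completed within 14 days before randomization, says: "The presence of angina will be assessed, and when present, classified according to the CCSC scale and documented on this form". The telephone follow-up says the same: "The presence of angina will be assessed by the DCC research nurse, and when present, classified according to the CCSC scale". Because a grade is given only when angina is present, no angina is a natural fifth category below grade I.

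**The concern.** A Pearson chi-squared test treats the five classes as unordered labels and spreads its power over 4 degrees of freedom. The clinical question is whether one arm has less angina than the other, which is mainly a one-directional question. A test that uses the ordering concentrates on that direction.

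Three things are given up:

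- power, if the arms differ by a general shift along the scale;
- a summary of how large the difference is, with a confidence interval;
- whatever precision the baseline class could add.

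At stake is a real reduction in angina being missed, or being reported as up to 11 separate p-values with no estimate attached.

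**Working it through.** **Inputs.** From the documents: 1:1 allocation; 2354 patients, so 1177 per arm; 15% loss to follow-up, so 1177 × 0.85 ≈ 1000 per arm at the end (deaths not removed); two-sided alpha 0.05. The documents give no expected CCSC distribution, effect size or power, so there is no figure of the plan's own to reproduce. Class mixes, odds ratios and correlations below are assumptions.

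**Step 1: loss without assuming a class mix.** Suppose an ordered 1-df test captures the whole difference, with noncentrality λ. Power on k df is P(χ²ₖ(λ) > cₖ), with c₁ = 3.84, c₃ = 7.81, c₄ = 9.49. For 80% power on 1 df, λ = (1.96 + 0.84)² ≈ 7.85. The same λ gives 59.5% on 4 df and 64.5% on 3 df. Repeating this:

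| Power of ordered test | Loss on 4 df (five categories) | Loss on 3 df (four categories) |
|---|---|---|
| 50% | 19 points | 15 points |
| 60% | 21 | 17 |
| 70% | 22 | 17 |
| 80% | 20 | 15 |
| 90% | 16 | 12 |
| 95% | 11 | 8 |
| 99% | 4 | 3 |

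In patients: 80% power on 4 df needs λ = 11.94, and 11.94 / 7.85 = 1.52, about 52% more. On 3 df it needs λ = 10.90, and 10.90 / 7.85 = 1.39.

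**Step 2: simulation of a proportional-odds shift.** 20,000 trials per setting, 1000 per arm, assumed comparator mix 70/15/9/4/2% (none, I-IV), Pearson against tie-corrected Wilcoxon:

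| Common odds ratio | Pearson | Wilcoxon | Loss |
|---|---|---|---|
| 1.15 | 17% | 30% | 13 |
| 1.20 | 28% | 47% | 19 |
| 1.25 | 41% | 63% | 22 |
| 1.30 | 55% | 75% | 21 |
| 1.40 | 78% | 92% | 14 |
| 1.50 | 91% | 98% | 7 |

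Check at 1.30: the angina-free odds 0.70/0.30 = 2.33 become 2.33 × 1.30 = 3.03, so the angina-free share rises to 75.2%. With the other classes shifted likewise, λ = 1000 × Σ(p − q)²/(p + q) ≈ 7.0, which gives about 54% on 4 df and 75% on 1 df, in line with the simulation. Across three assumed five-category mixes and both arm sizes the loss peaks at about 22 points and is 1-14 points at odds ratio 1.5. Two assumed four-category mixes peak at about 17 points.

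**Step 3: type I error.** With no difference between arms, Pearson rejects in 4.7-5.0% of simulated trials.

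**Step 4: a shift that is not proportional odds.** Assumed mixes: comparator 75/12/8/4/1%, other arm 75/16/6/2.5/0.5%. The angina-free share is equal and residual angina is milder; the cumulative shares are 75/87/95/99% against 75/91/97/99.5%, so the second arm is no worse at any cut-point. With 1000 per arm, λ = 1000 × (0.04²/0.28 + 0.02²/0.14 + 0.015²/0.065 + 0.005²/0.015) = 5.71 + 2.86 + 3.46 + 1.67 = 13.70, which is 86% power on 4 df. Simulation gives 86% for Pearson and 8% for the rank-sum test. Most rank information sits in the split between no angina and any angina, which is unchanged here.

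**Step 5: baseline adjustment.** Rank ANCOVA on baseline class, 2,000 trials per setting: a gain of about 0 points at a latent baseline-to-follow-up correlation of 0, 1-3 points at 0.2-0.3, and 5-8 points at 0.5.

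**The case against.** The strongest objection is Step 4: the advantage of the ordered test depends on the shape of the effect. If revascularization makes residual angina milder without changing how many patients are angina-free, replacing the chi-squared test outright could lose far more than it gains. This stands, and is why the chi-squared test should be kept as supportive.

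Second, the planned test is valid, CCSC is one of many secondary endpoints, the trial is not sized on it, and quality of life, the other part of the same objective, already has a longitudinal model. This also stands and limits the weight of the point.

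Third, a chi-squared test could mean a 1-df trend version. The plan does not say so, and the plain reading is Pearson. If a trend test is meant, the text should state it.

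Some stronger readings are tempting. A reader might infer that the plan forfeits a fixed amount of power, but without a stated class mix or effect the loss can only be given conditionally. A reader might infer that improvement and worsening cannot be told apart, but the class distribution is to be shown by arm, so direction will be visible; what is missing is an estimate and its interval. A reader might also infer that one mixed model over all visits is needed. Nothing above tests such a model. It would give a subject-specific odds ratio and would need a rule for deaths over five years.

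**Conclusion.** The point holds as a weakness of efficiency and reporting in one secondary endpoint. The CCSC comparison, as written, ignores the order of the scale, gives no effect estimate and leaves the collected baseline class unused.

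The loss is about 16-22 points on five categories, or 12-17 on four. It is conditional on an effect close to a proportional-odds shift and on an ordered test with 50-90% power; it is smaller for very small or large effects. Baseline adjustment would add perhaps 0-8 points, depending on a correlation the documents do not give. For some non-proportional effects the comparison reverses. Type I error at each visit and the primary analysis are not affected.

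**What to change.** In the Analytical Plan, Health Status, make the CCSC comparison at each visit a proportional-odds regression with no angina as the lowest category, adjusted for baseline CCSC class and for the prior-PCI and vessel-type randomization strata. Report the common odds ratio with its 95% CI. State that the result describes patients alive and assessed at that visit. Keep the class tables by arm, and keep the chi-squared test as supportive, with its categories and degrees of freedom stated.

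The cost is SAP wording; no new visits, forms or patients are needed. The downside is reliance on approximate proportional odds, with low power when the arms differ mainly in severity among patients who still have angina (8% against 86% in the assumed example). The retained chi-squared test and tables guard against overlooking that pattern.
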